## **6.1 DETERMINATION OF SAMPLE SIZE**

The sample size was determined by practical considerations and not based on statistical power calculations. Approximately four subjects will be enrolled in SAD cohort 1 (2 active treatment and 2 placebo). Approximately twelve subjects will be enrolled in each of the other SAD and MAD cohorts. They will be randomized to either active treatment (10 subjects per dose level) or placebo (2 subjects per dose level).

With ten subjects on active drug per dose group or cohort, there is a 94% chance to observe at least one AE that has an incidence rate of 25% in the population.

## **6.2 SUMMARIES OF CONDUCT OF STUDY**

The number of study subjects who enroll, discontinue, or complete the study will be summarized by treatment (RO7049389 vs. matching placebo) for each dose cohort in the study. Reasons for premature study withdrawal will be listed and summarized by treatment and dose cohort. Enrollment and protocol deviations will be listed and evaluated for their potential impact on interpretation of study results. Study drug administration (RO7049389 or matching placebo) will be summarized with number of doses and percentage of assigned dose subjects received by treatment and dose cohort.

## **6.3 ANALYSIS POPULATIONS**

### **6.3.1 Safety Analysis Population**

All study subjects who have received at least one dose of the study medication (RO7049389 or matching placebo), whether prematurely withdrawn from the study or not, and with at least one safety assessment, will be included in the safety analysis.

### **6.3.2 Pharmacokinetic Analysis Population**

Study subjects will be excluded from the pharmacokinetic analysis population if they significantly violate the inclusion or exclusion criteria, deviate significantly from the protocol or if data are unavailable or incomplete which may influence the pharmacokinetic analysis. Excluded cases will be documented together with the reason for exclusion. All decisions on exclusions from the analysis will be made prior to database closure.

## **6.4 SUMMARIES OF TREATMENT GROUP COMPARABILITY**

Study subjects randomized to receive placebo will be pooled together to form a pooled placebo group. Demographic and baseline characteristics (age, sex, etc.) will be summarized by treatment (each dose level of RO7049389 vs. pooled placebo group) for the safety population using descriptive statistics. For continuous variables, mean, standard deviation, median, and ranges will be presented. For categorical data, the

**RO7049389—F. Hoffmann-La Roche Ltd**  
63/Protocol YP39406, Version 4

proportion of subjects in each category will be summarized. Summaries will be presented in overall and by cohorts.

## **6.5 SAFETY ANALYSES**

All safety analyses will be based on the safety analysis population. Subjects will be grouped based on the treatment they actually receive. Safety will be assessed through physical exams, adverse events, changes in laboratory results, changes in ECG measurements, and changes in vital sign measurements.

### **6.5.1 Adverse Events**

The original terms recorded on the eCRF by the Investigator for adverse events will be standardized by the Sponsor.

Adverse events will be summarized by MedDRA coded term. In addition, adverse events will be summarized by their toxicity level (according to the maximum reported severity level) and severity (severe vs. non-severe). All serious adverse events, including deaths, severe adverse events (Grade  $\geq 3$ ), and adverse events of special interest will be listed and summarized separately. Adverse events leading to study drug discontinuation or interruption will be summarized as well. Subjects will be tabulated by treatment (RO7049389 vs. pooled placebo group) and dose level.

### **6.5.2 Clinical Laboratory Test Results**

All clinical laboratory data will be stored on the database in the units in which they were reported. Study subject listings and summary statistics at each assessment time will be presented using the International System of Units (SI units; Système International d'Unités). Laboratory data not reported in SI units will be converted to SI units before processing.

Laboratory test values will be presented by individual listings with flagging of values outside the normal ranges.

The proportion of study subjects with laboratory abnormalities will be summarized by treatment (RO7049389 vs. pooled placebo group) and dose level. Additionally, the absolute value and change from baseline in all laboratory tests will be summarized by treatment and visit using descriptive statistics.

#### **6.5.2.1 Standard Reference Ranges and Transformation of Data**

Roche standard reference ranges, rather than the reference ranges of the Investigator, will be used for all parameters. For most parameters, the measured laboratory test result will be assessed directly using the Roche standard reference range. Certain laboratory parameters will be transformed to Roche's standard reference ranges.

A transformation will be performed on certain laboratory tests that lack sufficiently common procedures and have a wide range of investigator ranges, e.g., enzyme tests

**RO7049389—F. Hoffmann-La Roche Ltd**  
64/Protocol YP39406, Version 4

that include AST, ALT, and alkaline phosphatase and total bilirubin. Since the standard reference ranges for these parameters have a lower limit of zero, only the upper limits of the ranges will be used in transforming the data.

#### **6.5.2.2      Definition of Laboratory Abnormalities**

For all laboratory parameters included, there exists a Roche predefined standard reference range. Laboratory values falling outside this standard reference range will be labeled “H” for high or “L” for low in study subject listings of laboratory data.

In addition to the standard reference range, a marked reference range has been predefined by Roche for each laboratory parameter. The marked reference range is broader than the standard reference range. Values falling outside the marked reference range that also represent a defined change from baseline will be considered marked laboratory abnormalities (i.e., potentially clinically relevant). If a baseline value is not available for a study subject, the midpoint of the standard reference range will be used as the study subject’s baseline value for the purposes of determining marked laboratory abnormalities. Marked laboratory abnormalities will be labeled in the study subject listings as “HH” for very high or “LL” for very low.

#### **6.5.3      Vital Signs**

Vital signs data will be presented by individual listings with flagging of values outside the normal ranges and flagging of marked abnormalities. In addition, tabular summaries will be used, as appropriate.

#### **6.5.4      ECG Data Analysis**

ECG data will be presented by individual listings with flagging of values outside the normal ranges and flagging of marked abnormalities. In addition, tabular summaries will be used, as appropriate.

Summary descriptive statistics for the actual values and changes from baseline will be tabulated by nominal time for HR, QRS duration, PR and QTcF (see [Appendix 5](#)). For multiple measurements taken at a nominal time-point, the average of these measurements will be used as the value at that nominal time-point in all summaries. In addition, QTcF will be categorized at each time-point as  $\leq 450$  msec,  $> 450-480$  msec,  $> 480-500$  msec and  $> 500$  msec and summarized. Similarly, a summary will be provided of the QTcF changes from baseline at each time-point categorized as  $< 30$  msec, 30-60 msec, and  $> 60$  msec. Changes of the overall ECG interpretation, T-wave and U-wave morphology will be summarized.

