#### **3.1.2.1 Dose-Escalation Stopping Rules**

Any serious adverse event considered related to study drug will lead to an immediate halt of study drug dosing, dose escalation and enrollment of new subjects until a thorough investigation has been conducted by the Sponsor's Clinical Team and the Principal Investigator. The sponsor or designee will notify all investigators and IRBs/EC, if required (see Section [5.3](#)), regarding the outcome of such investigation. The study will only continue if agreed by the IRBs/EC.

An internal safety review of the unblinded data by Sponsor representatives from Translational Medicine, Drug Safety, Clinical Pharmacology and Biostatistics will be performed prior to each RO7049389 dose-escalation.

Planned dose-escalation will not be implemented if one of the following circumstances occurs in subjects treated with RO7049389, unless it is obvious that the occurrence is not related to the administration of study medication:

- If at any dose level, more than two subjects on active drug experience:
  - Severe and clinically significant (as defined by the Investigator) RO7049389-related AEs of the same character.

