**RO7049389—F. Hoffmann-La Roche Ltd**

31/Protocol YP39406, Version 4

- Clinically significant RO7049389-related laboratory abnormalities of the same character (e.g., ALT or AST $>3\times$ ULN, and total bilirubin $>2\times$ ULN).
- Clinically significant RO7049389-related changes in vital signs or ECGs of the same character (e.g., QTcF $>500$  msec, or  $>60$  msec longer than the pre-dose baseline, within the first 48 hours post-dose).
- It is predicted that further dose-escalation will not result in a further increase in plasma exposure.

- The proposed dose *or exposure* exceeds those previously evaluated in the study YP39364.
- Other findings (regardless of the incidence rates) that at the joint discretion of the Sponsor and the Investigator indicate dose-escalation should be halted.

If dose-escalation is stopped, lower doses within the tolerated dose range could be investigated, or a dose repeated in the subsequent cohorts by mutual agreement between the Sponsor and Investigator, in order to increase the amount of data within this tolerated dose range.

For an individual subject, dosing should not continue if there are:

- Clinically significant RO7049389-related changes in safety parameters that are considered not acceptable by the Investigator and/or the Sponsor; or
- Poor gastrointestinal (GI) tolerability that is considered to affect the subject's wellbeing and/or the PK evaluation.

Due to the exploratory nature of this clinical study, its conduct can be discontinued at any time at the discretion of the Sponsor. This will not constitute a premature termination of the study.

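### The planned QTcF outlier tables count subjects only within each time-point, so no planned table gives the number of distinct subjects who ever crossed a limit

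*Combined protocol and SAP*

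**What the plan says.** Section 6.5.4 defines two categorical QTcF summaries. For absolute values, "QTcF will be categorized at each time-point as" at most 450, above 450 to 480, above 480 to 500, and above 500 msec. For changes, "a summary will be provided of the QTcF changes from baseline at each time-point categorized as" below 30, 30 to 60, and above 60 msec. Both use the replicate mean: "the average of these measurements will be used as the value at that nominal time-point in all summaries".

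Two other ECG outputs are named in that section. The first is subject-level: "ECG data will be presented by individual listings with flagging of values outside the normal ranges and flagging of marked abnormalities". The second is open-ended: "In addition, tabular summaries will be used, as appropriate". Neither there nor elsewhere in the protocol is there a table by each subject's highest post-dose value.

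Other safety data are summarised per subject. In Section 6.5.2, "The proportion of study subjects with laboratory abnormalities will be summarized by treatment" and dose level. Section 6.5.1 takes each adverse event at its maximum reported severity. The escalation criterion in Section 3.1.2.1 also counts subjects ("If at any dose level, more than two subjects on active drug experience" one of the listed findings, among them "Clinically significant RO7049389-related changes in vital signs or ECGs of the same character"). Its ECG examples are QTcF above 500 msec or more than 60 msec over the pre-dose baseline in the first 48 hours.

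**The concern.** The usual question about QTcF outliers is how many subjects on each dose ever exceeded a limit, and how that compares with placebo. Rows split by time do not answer it. The largest row is only a lower bound on the number of subjects, and adding rows counts anyone with a sustained prolongation more than once.

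ECGs are one of the four safety outcome measures, and the primary objective is safety and tolerability compared with placebo. Section 6 makes all analyses descriptive, so the tables carry the conclusion. With 10 active subjects per dose, the difference between one subject and three is the difference between 10% and 30%.

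**Working it through.** **The plan's own figure.** Section 6.1 gives a 94% chance of seeing at least one adverse event of 25% incidence among 10 active subjects: 1 − 0.75^10 = 0.9437. It reproduces and is not in dispute. It is a statement about subjects, which is the unit missing from the QTcF categories. The plan gives no figure for QTcF outliers.

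**Inputs from the protocol.** Ten active subjects per dose in Cohorts 2 to 4 (Section 6.1); categories by time-point (Section 6.5.4). The number of ECG time-points, T, is not in the available text and is an assumption wherever it appears below.

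**What the rows determine.** Let n_t be the number of subjects above a limit at time t, and N the number of distinct subjects ever above it. The rows fix only

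max(n_t) ≤ N ≤ min(10, sum of n_t).

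Suppose three rows read 1/10 and the rest 0/10. Then 1 ≤ N ≤ 3, and both ends are attainable:

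| Pattern | Rows above +60 msec | Distinct subjects |
|---|---|---|
| A at +64, B at +66, C at +62, at three different times | 1, 1, 1 | 3/10 = 30% |
| One subject above +60 at all three times | 1, 1, 1 | 1/10 = 10% |

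The rows are the same and the incidence differs threefold. This needs no assumption about the drug or the schedule.

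**How often it would happen.** Suppose exactly three subjects cross, at random times. If each crosses at one time-point, the chance that no row shows three is 1 − 1/T². If each crossing lasts two consecutive time-points, the chance comes from enumerating the (T − 1)³ sets of starting times.

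| T (assumed) | One time-point each | Two consecutive |
|---|---|---|
| 3 | 88.9% | 0% |
| 4 | 93.8% | 44.4% |
| 6 | 97.2% | 76.8% |
| 8 | 98.4% | 87.5% |
| 10 | 99.0% | 92.2% |

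The result runs from 0% to 99% on two unknowns. Random timing is also unlike a drug effect, whose peak is tied to dosing and would cluster. The table shows why no single percentage should be quoted.

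**Placebo available.** With two placebo subjects per cohort, the pool is up to 4 × 2 = 8 in SAD and up to 3 × 2 = 6 in MAD, if all optional parts are run.

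**Noise in a maximum.** Assume no drug effect, independent errors, one pre-dose baseline, 8 to 12 post-dose time-points and a within-subject SD of 7 to 10 msec for a triplicate mean. The expected number of 10 subjects whose maximum increase exceeds 30 msec is then 10 × [1 − E{Φ((30 + b)/SD)^T}], with b the baseline error. This gives 0.1 (SD 7) to 1.2 (SD 10, T = 12). Above 60 msec it is about 0.001 or less.

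**The case against.** The strongest objection is that nothing is lost. The values stay in flagged individual listings, and with 10 active subjects per dose a reader can count distinct subjects by hand. Section 6.5.4 also allows further tables where appropriate, and by-time display is a legitimate choice: each row is correct for what it reports. All of this is true. It limits the weight of the point, but a permitted table is not a committed one, and the listings give no incidence against placebo.

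A reader might go further and infer that the stopping rule could be missed, since it turns on more than two subjects and uses the same 500 and 60 msec limits. The documents do not support that:

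- Section 4.5.1.4 (item 10) requires a repeat ECG within 5 minutes and Sponsor notification when a subject crosses either limit, then at least hourly repeats if confirmed. Patients A, B and C in the example would each be notified.
- Section 4.2.1 has individual data reviewed before each escalation, and Section 3.1.2.1 adds a Sponsor review of unblinded data.
- The rule also requires clinical significance, relation to RO7049389 and the same character, and gives the msec limits only as examples. Neither the by-time table nor a worst-value table carries those judgements.

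A large QTcF effect would also probably show in the by-time mean changes that Section 6.5.4 already plans. What is at risk is a count of subjects; detection of a strong signal is much less so.

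Lastly, maxima are raised by noise. That stands, and is a reason to read them beside placebo and to keep the by-time table.

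**Conclusion.** The point holds as a weakness of the summary table. As specified, the per-subject incidence of QTcF outliers by dose against pooled placebo appears in no planned table and cannot be derived from the planned rows. In the worked example three of 10 subjects (30%) appear as at most 1/10 in any row. That this can happen follows from counting alone. How often it would happen rests on the ECG schedule and the duration of effect, neither of which is in the available text, so no frequency is claimed. No data are lost and no escalation decision depends on the table. It is a cheap improvement to the reporting of a primary safety outcome.

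**What to change.** In Section 6.5.4 add, separately for SAD and MAD, the number and proportion of subjects by (a) maximum post-dose QTcF and (b) maximum increase from that phase's pre-dose baseline. Use the existing cut-offs and present by dose level and pooled placebo. State whether unscheduled and repeat ECGs count towards the maximum: Section 4.5.1.4 calls for such recordings, but Section 6.5.4 gives no rule for placing them in nominal-time rows. Keep the by-time-point tables as supportive.

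The cost is a few lines of text and one extra table per phase, from data already collected. The downside is the upward pull of noise on a maximum, so active and placebo subjects should be compared over the same scheduled times. The placebo pool is small, so the comparison stays descriptive.

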#### **6.5.5      Concomitant Medications**

The original terms recorded on the study subjects’ eCRF by the Investigator for concomitant medications will be standardized by the Sponsor by assigning preferred terms.

**RO7049389—F. Hoffmann-La Roche Ltd**  
65/Protocol YP39406, Version 4

Concomitant medications will be presented in summary tables and listings.

## **6.6 PHARMACOKINETIC ANALYSES**

Non-compartmental analysis will be employed for estimation of PK parameters.

Individual plasma concentrations at each sampling time-point for RO7049389 of each cohort will be presented by listings and appropriate descriptive summary statistics, including means, medians, geometric means, ranges, standard deviations and coefficients of variation. Individual and mean plasma concentration of each cohort versus time data will be plotted on semi-logarithmic scales.

All PK parameters will be presented by individual listings and summary statistics for each cohort including means, geometric means, medians, ranges, standard deviations and coefficients of variation.

The relationship of selected PK parameters from Day 1 with dose will be evaluated graphically to establish dose-linearity. Dose-proportionality may be assessed by estimating the slope of the linear regression of logarithmically transformed variables  $C_{\max}$ ,  $AUC_{0-\text{last}}$  and  $AUC_{0-\infty}$  versus the logarithmically transformed dose. A 95% confidence interval for the slope which includes the value 1 would be consistent with dose-proportionality.

Plasma samples collected in the study will be qualitatively and/or quantitatively analyzed for the presence of metabolites of RO7049389.

A population PK model development and analysis may be performed. The Population PK results will be reported in a separated document.

## **6.7 INTERIM ANALYSIS**

No interim analysis is planned for this study.

# **7. DATA COLLECTION AND MANAGEMENT**

## **7.1 DATA QUALITY ASSURANCE**

The Sponsor will be responsible for data management of this study, including quality checking of the data. Sites will be responsible for data entry into the Electronic Data Capture (EDC) system.

A comprehensive validation check program will verify the data. Discrepancies will be generated automatically in the system at the point of entry or added manually for resolution by the Investigator.

The Sponsor will produce a Data Handling Manual and a Data Management Plan that describes the quality checking to be performed on the data. Laboratory electronic data

**RO7049389—F. Hoffmann-La Roche Ltd**  
66/Protocol YP39406, Version 4

will be sent directly to the Sponsor, using the Sponsor's standard procedures to handle and process the electronic transfer of these data.

System backups for data stored by the Sponsor and records retention for the study data will be consistent with the Sponsor's standard procedures.

## **7.2 ELECTRONIC CASE REPORT FORMS**

Data for this study will be captured via an on line EDC system. The data collected in the source documents is entered onto the study eCRF. An audit trail will maintain a record of initial entries and changes made; reasons for change; time and date of entry; and user name of person authorizing entry or change. For each study subject enrolled, an eCRF must be completed and electronically signed by the Principal Investigator or authorized delegate from the study staff. If a study subject withdraws from the study, the reason must be noted on the eCRF. If a study subject is withdrawn from the study because of a treatment-limiting adverse event, thorough efforts should be made to clearly document the outcome.

The Investigator should ensure the accuracy, completeness and timeliness of the data reported to the Sponsor/CRO in the eCRFs and in all required reports.

eCRFs will be submitted electronically to the Sponsor/CRO and should be handled in accordance with instructions from the Sponsor/CRO.

At the end of the study, the Investigator will receive subject data for his or her site in a readable format on a compact disc that must be kept with the study records.

Acknowledgement of receipt of the compact disc is required.

## **7.3 SOURCE DATA DOCUMENTATION**

Study monitors will perform ongoing source data verification to confirm that critical protocol data (i.e., source data) entered into the eCRFs by authorized site personnel are accurate, complete, and verifiable from source documents.

Source documents (paper or electronic) are those in which subject data are recorded and documented for the first time. They include, but are not limited to, hospital records, clinical and office charts, laboratory notes, memoranda, subject -reported outcomes, evaluation checklists, pharmacy dispensing records, recorded data from automated instruments, copies of transcriptions that are certified after verification as being accurate and complete, microfiche, photographic negatives, microfilm or magnetic media, X-rays, subject files, and records kept at pharmacies, laboratories, and medico-technical departments involved in a clinical trial.

Before study initiation, data to be entered directly into the eCRFs (i.e., no prior written or electronic record of the data) and considered source data must be defined in the Trial Monitoring Plan.

**RO7049389—F. Hoffmann-La Roche Ltd**  
67/Protocol YP39406, Version 4

Source documents that are required to verify the validity and completeness of data entered into the eCRFs must not be obliterated or destroyed and must be retained per the policy for retention of records described in Section 7.5.

To facilitate source data verification, the investigators and institutions must provide the Sponsor direct access to applicable source documents and reports for trial-related monitoring, Sponsor audits, and IRB/EC review. The investigational site must also allow inspection by applicable Health Authorities.

